### Secondary Objectives:

- To evaluate optimal strength (1.5 vs. 2.0 vs. 2.5 mA) in tDCS application for DLPFC engagement. Analogous to dose-finding in drug studies, we will conduct a parametric test for optimal current strength.
- To investigate the tolerability and feasibility of multi-session tDCS in schizophrenia. There is extensive evidence for tolerability of tDCS, confirmation for schizophrenia will be explicitly evaluated.

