### Hypothesis

The primary hypothesis to be tested in this study is observing positive modulations in fMRI BOLD signals in the DLPFC and EEG frontal gamma oscillations during a cognitive control task following frontal tDCS modulation. We hypothesize tDCS application at 2.5 mA will show greatest engagement of DLPFC and frontal gamma oscillations and that 80% of subjects will complete the full tDCS protocol.

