**Day 1:** Experimenters will perform baseline fMRI and EEG procedures. Cognitive effects will be evaluated to assess acute effects of tDCS compared to baseline and to evaluate persistence. Subjects will undergo MRI in order to assist localization of EEG data and provide independent and complementary correlates of tDCS effects.

**Day 2- 6:** During these visits, the participants will undergo two 20 minute daily tDCS sessions, separated by 1 hour, for 5 consecutive days. Tolerability assessment will be administered to gauge how tolerable the tDCS session for the participant. Comprehension assessment will be administered to gauge the patients understanding of the study and to ensure they still have informed consent.

**Week 1:** Experimenters will perform posttest fMRI and EEG procedures. Cognitive effects will be evaluated to assess effects of tDCS compared to baseline and to evaluate persistence. Subjects will undergo MRI in order to assist localization of EEG data and provide independent and complementary correlates of tDCS effects.

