## **TREATMENT ALLOCATION AND BLINDING**

### **Randomization, Blinding and Tolerability Assessments**

Subjects will be randomly assigned to one of the three active tDCS (1.5 mA, 2.0 mA or 2.5 mA) or sham groups (N=25/group), under the constraint of group-level demographic and cognitive status matching. For robust blinding, we will coordinate three different teams of experimenters, responsible for 1) clinical/neuropsychological status evaluations; 2) tDCS application; and 3) EEG/fMRI recording and data analysis. Critical to our third aim, the second team will be responsible for assessing tolerability during the stimulation and general adherence to the stimulation sessions. We will employ a “triple-blind design” in the following manner to minimize unintended biases/confounds: randomized group assignment; automatic, computer control of the stimulator according to the encrypted subject’s group; de-identified data analysis.

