### **STATISTICAL METHODS**

**Primary Objective:** Dependent measures will be task condition-related differences in fMRI BOLD activation as measured through GLM and EEG oscillatory activity in the gamma band as analytically estimated by complex wavelet transformation. Group and time point differences will first be assessed with omnibus tests instantiated through the general linear model (e.g., repeated measures ANOVA) to determine the presence and direction of potential effects. Effects equivalent to  $f \geq .16$  will be targeted. To determine the efficacy of the treatment conditions, we plan to conduct post-hoc comparisons of the post- minus pre-test differences between each active stimulation group and the sham stimulation group, as well as within each group between the post- and pre-test measures. The behavioral context of these changes will also be assessed by the Inc-Con difference in accuracy and reaction time in an analogous manner to fMRI and EEG measures.

**Secondary Objective:** Initial analytical targets will be identified concurrent with Aim 1. Polynomial trend analyses will be used to determine the dose-response curve to tDCS. To assess the degree of efficacy of each treatment, Cohen's  $d_z$ , a measure of effect size similar to Cohen's  $d$  which also accounts for the covariance between measures, will be calculated within each group based on the difference between control-related activations from the pre- and post-test assessments with an ideal target of  $d_z = .534$  for fMRI BOLD activation and  $d_z = .687$  for EEG gamma synchrony (i.e., half the observed distance between patient and control measures based on preliminary data). As an exploratory analysis, we will also make use of the structural MRIs to create individualized head models of current strength in the DLPFC. Since the current strength, distribution and even polarity can vary considerably as a function of individual physiology and anatomy, such comparisons between the predictive value of the tDCS device's current output vs. the modeled current strength in relation to the fMRI

and EEG measures will be invaluable in informing future investigations of personalized treatment protocols and tDCS tolerability/safety.

**Tertiary Objective:** A target completion rate of 80% serves as our benchmark for assessing feasibility. No analysis is required - this benchmark will simply serve as the required threshold for starting the R33 phase.

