**R61 to R33 Phase Transition Criteria:** Our 'Go/No-go' strategy for this transition will require an effect size of tDCS to be  $f \geq .16$  for both DLPFC BOLD signal and frontal EEG gamma activity. After confirming that this effect is driven by tDCS effects in a positive direction, the current strength that has the highest effect size *and* also meets >80% completion rate will be the one that is selected for the R33 phase.

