### **Quality Control and Assurance**

The study will be monitored by a Data Safety Monitoring Board (DSMB). The DSMB will independently review the protocol and consent documents, AEs, and outcome data as needed, for the proposed study. The DSMB will evaluate issues related to subject safety and the adequacy and integrity of accumulated data. The DSMB will meet once for every 20 subjects who have completed the study to review the study. Data reports will be prepared by [name] study coordinator to support the work of the DSMB.

The study coordinator will create tables for the DSMB to review. The tables will include enrollment, demographic information by treatment arm, abnormal laboratory results, SAEs, and missing data. After each meeting, the DSMB will issue a memo documenting any action items for the team. Copies will be provided to the Baylor IRB upon request.

[name] lab will conduct routine (bimonthly) reviews of consistency, reliability and accuracy of data collected for any paper records. Similar checks for any data in electronic form will also be conducted but in an automated fashion (e.g checking for accurate time/date stamps, file sizes etc.).

**Stopping Rules:** Participants must complete the 5 consecutive days of tDCS treatment within a maximum of 6 consecutive days. Appointments will be scheduled for 5 consecutive days however, if a participant misses an appointment we will only allow one day to be rescheduled. If the 5 sessions are not completed within the 6 days allotted the participant will be withdrawn from the study.

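### Tolerability is a stated objective with daily ratings, but the only statistical provision for it is a completion benchmark that also counts missed appointments

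*Combined protocol and SAP*

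**What the plan says.** The Background makes confirming tolerability part of the goal of the R61 phase. The Secondary Objectives list tolerability together with feasibility and say: "There is extensive evidence for tolerability of tDCS, confirmation for schizophrenia will be explicitly evaluated".

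The data are to be collected. Table 1 schedules a tolerability assessment on Days 2 to 6, and the Day 2-6 text says: "Tolerability assessment will be administered to gauge how tolerable the tDCS session for the participant". No arm is exempted. The section on randomization, blinding and tolerability gives the tDCS team responsibility for "assessing tolerability during the stimulation and general adherence to the stimulation sessions", calls this critical to the third aim, and so treats tolerability and adherence as two different things.

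The statistical provision for that aim is the Tertiary Objective paragraph of the Statistical Methods: "A target completion rate of 80% serves as our benchmark for assessing feasibility", followed by "No analysis is required - this benchmark will simply serve as the required threshold for starting the R33 phase". The R61 to R33 transition criteria then require that the chosen current "also meets >80% completion rate will be the one that is selected for the R33 phase". The Hypothesis section puts the same target as "80% of subjects will complete the full tDCS protocol".

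A participant can become a non-completer without any discomfort. Under Poor Adherence, a second missed tDCS appointment ends participation. Under Stopping Rules: "If the 5 sessions are not completed within the 6 days allotted the participant will be withdrawn from the study".

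**The concern.** The protocol sets out to learn whether each current is tolerated and measures this daily, but the analysis section contains nothing that uses the measurements. What it does contain, completion, answers a different question: whether participants got through the schedule. Attendance and tolerance both feed into it, and no section separates non-completions by cause or compares them with sham.

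Two misreadings could follow at the end of R61. A current with low completion could be described as poorly tolerated when the losses were scheduling losses. A current with high completion could be described as well tolerated although participants finished in marked discomfort. In both cases the ratings that could settle the matter have no pre-specified summary, so how they are reported would be chosen after the data are seen.

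**Working it through.** **1. Does any other section supply the analysis?** The places where tolerability could be analysed are these:

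- *Primary Objective (Statistical Methods):* fMRI, EEG and task behaviour only.
- *Secondary Objective (Statistical Methods):* trend analysis and effect sizes for fMRI and EEG. Tolerability is mentioned at the end of the head-model paragraph, but as something future studies may learn about. The comparison described there uses the fMRI and EEG measures.
- *Tertiary Objective:* the completion benchmark, with no analysis.
- *Assessment of Risk and Safety; Quality Control and Assurance:* weekly team review and DSMB oversight of adverse events. The listed DSMB tables cover enrolment, demographics by arm, laboratory abnormalities, SAEs and missing data, and do not list the ratings.

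None summarises the ratings or compares them across arms.

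**2. The plan's own figure.** The 80% benchmark is a fixed threshold. It is not derived from an alpha, a power or an expected rate, so there is nothing to reproduce. With 4 × 25 = 100 participants, it means at least 0.80 × 25 = 20 completers per arm under the Statistical Methods wording, and at least 21 under the >80% transition criterion.

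**3. Completion cannot identify its cause.** Let t be the share lost to intolerance and a the share lost to attendance, treated as independent: completion = (1 − t)(1 − a). Both are assumed, since the documents give neither.

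- t = 0, a = 0.20: completion 0.80.
- t = 0.20, a = 0: completion 0.80.

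The chance of at least 21 of 25 completers is 0.42 in both cases. One current is stopped for intolerance by nobody and the other by one participant in five, yet the benchmark treats them alike. With t = 0.10 and a = 0, that chance is 0.90.

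**4. How far attendance alone could move completion (illustration).** Assume each visit is missed independently with probability m, and one missed visit may be made up if the make-up is attended:

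P(complete) = (1 − m)^5 + 5m(1 − m)^4 × (1 − m)

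| m (assumed) | P(complete) | lost through attendance |
|---|---|---|
| 5% | 0.774 + 0.193 = 0.967 | 3.3% |
| 10% | 0.590 + 0.295 = 0.886 | 11.4% |
| 15% | 0.444 + 0.333 = 0.776 | 22.4% |

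At 15% per visit, completion is expected to fall below 80% with no intolerance at all.

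**5. What 25 per arm can say.** An observed 21/25 has an exact 95% interval of 64% to 95%. No intolerance stops in 25 gives an exact upper limit of 1 − 0.025^(1/25) = 13.7%. For a mean rating compared with sham (25 v 25), the 95% half-width is about 2.01 × √(2/25) = 0.57 SD. At two-sided 0.05, power is about 81% for a 0.8 SD difference and 42% for 0.5 SD. For intolerance of 5% v 20% (assumed) it is 36%. This supports estimates with intervals, not a test that decides the matter.

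**The case against.** The strongest reply is that the sentence saying no analysis is needed refers to checking a fixed feasibility threshold. It does not say that the ratings will be ignored, and it does not offer completion as the measure of tolerability. That is a fair reading. On it, however, tolerability has no criterion and no analysis of its own, although the objectives promise an explicit evaluation.

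A reader might go further and infer that the trial cannot say whether a current is tolerated. The documents do not support that. Daily ratings, a sham arm and adverse-event review will all exist, and severe intolerance can lead to withdrawal and so reach the completion count. What is missing is a planned analysis.

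A reader might also infer that counting missed visits is a flaw in the R33 gate, or that the attendance figures show how often the fix would rescue a well-tolerated current. Neither follows. The objective covers feasibility as well as tolerability, and a regimen that participants do not attend fails on feasibility whatever the cause. The gate would work the same way after the fix. The miss rates are also assumed, and the protocol lists measures to limit attrition.

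Two cautions about a sham comparison stand. Sham includes fade-in, fade-out and brief low-current pulses, so it is not free of stimulation. Tingling and itching are expected, so a difference from sham is not in itself intolerance. That a participant who resumes after an interruption would count as a completer is an inference, because completion is not defined at that level.

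**Conclusion.** The point holds: as written, the tolerability part of the third aim is answered only by a rate that mixes intolerance with missed appointments, and no planned analysis can say whether each current is tolerated. This rests on the text and not on any assumed rate. The 3%, 11% and 22% attendance losses depend on assumed, independent miss rates of 5%, 10% and 15% per visit. They show only that completion can fall without intolerance.

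The sponsor should make the change. It concerns a secondary objective, needs no new data, and matters most if settled before unblinding. The 80% and >80% wordings differ by one participant per arm (20 or 21 of 25) and must be reconciled.

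**What to change.** In the Tertiary Objective paragraph, replace the statement that no analysis is required with:

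1. A summary of the daily tolerability ratings by arm over the five treatment days, with the estimated difference of each active current from sham and its 95% confidence interval. Present it as estimation, state that 25 per arm is imprecise and that sham is not stimulation-free, and name the rating instrument and scale.
2. A table by arm of non-completions, and of sessions interrupted for discomfort, each classified as tolerability-related or as attendance/other.

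Base the tolerability statement on (1) and (2). Keep completion as the feasibility gate for R33, state its definition and denominator (randomised or started tDCS), and reconcile 80% in the Tertiary Objective with >80% in the transition criteria.

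Cost: a little extra analysis, and a reason code on existing discontinuation and session forms, completed by the tDCS team that already records tolerability and adherence. No new visits or assessments, and no change to withdrawal rules.

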**BACKGROUND**

[figure not shown]
This protocol is supported by a NIMH award that is organized into two phases. The goals of the first (R61) and second (R33) phases are to demonstrate target engagement and then clinical effect by the therapeutic intervention, respectively. Specifically, the primary goal of the R61 phase is to employ multimodal imaging to explicitly test for the assumed DLPFC engagement (fMRI) and modulation of frontal gamma activity (EEG) by tDCS, investigate the optimization of tDCS application parameters, and confirm the tolerability of tDCS for schizophrenia patients, and will be the focus of this protocol. After confirming that this effect is driven by tDCS effects in a positive direction, the current strength that has the highest effect size and also meets >80% completion rate will be the one that is selected for the R33 phase, which will seek to demonstrate clinical effect by assessing clinical outcomes scales and observing improvements in cognitive control mediated by DLPFC and frontal gamma oscillation engagement.

A successful outcome of this study would provide tDCS the sound mechanistic, methodologic and clinical-relevance basis for more definitive testing in large-scale clinical trials as a highly innovative therapeutic intervention for cognitive impairments in schizophrenia.

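### The R33 Go bar of f ≥ .16 leaves its formula and its directional contrast open, and it misfires on either usual formula

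*Combined protocol and SAP*

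**What the plan says.** The R61 to R33 Phase Transition Criteria (Statistical Methods) state: "Our 'Go/No-go' strategy for this transition will require an effect size of tDCS to be" f ≥ .16 for both DLPFC BOLD and frontal EEG gamma. The rule then continues: "After confirming that this effect is driven by tDCS effects in a positive direction, the current strength that has the highest effect size", provided that the current also meets a completion rate above 80%, goes forward to R33. The Background section repeats the selection rule: "the current strength that has the highest effect size and also meets >80% completion rate will be the one that is selected".

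The only other use of f is under Primary Objective, where f ≥ .16 is the effect targeted. The model is described there as follows: "Group and time point differences will first be assessed with omnibus tests instantiated through the general linear model (e.g., repeated measures ANOVA". Its purpose is "to determine the presence and direction of potential effects". Two sets of follow-up comparisons are planned. One is sham-controlled: "post-hoc comparisons of the post- minus pre-test differences between each active stimulation group and the sham stimulation group". The other has no sham control and is described with the words "as well as within each group between the post- and pre-test measures".

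Under Secondary Objective, the degree of efficacy of each treatment is measured by Cohen's dz, which "will be calculated within each group based on the difference between control-related activations from the pre- and post-test assessments with an ideal target of" .534 for BOLD and .687 for gamma.

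No section says which model term f belongs to, how f is calculated, which comparison must be positive, or how two measures yield one highest effect size.

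**The concern.** The bar is applied to an observed f, so the formula is part of the decision rule. Partial f divides the effect by the error of the change scores. Cell-mean f divides it by the spread between patients within a cell, and therefore depends on the pre-post correlation. The same data can clear .16 on one and miss it on the other.

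A group-by-time F on 3 degrees of freedom has no sign, so direction has to come from a named contrast. The plan offers a sham-controlled one and an uncontrolled one and does not choose. Its efficacy measure for each current, the within-group dz, is the uncontrolled kind, so practice or regression to the mean would count towards it.

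At stake are the start of R33 and the current taken into it. As written, the reading could be settled after the results are seen.

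**Working it through.** **Inputs from the protocol.** Four groups of 25 (Overview of Study Design); one baseline and one post-test (Objectives and Hypotheses); bar f = .16; dz targets .534 and .687 (Statistical Methods). The documents give no alpha, power or sample-size calculation for this bar, so there is no stated figure to reproduce.

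**Assumed, because not in the documents.** Group-by-time term; 25 analysed per arm; all arms meet the completion criterion; BOLD-gamma correlation 0 to .5 (this gives the ranges); pre-post correlation r as stated. At target means all three active arms at the dz targets and sham unchanged. Joint rates come from simulated trials and are good to about one percentage point.

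**1. Partial f with no effect.** f = sqrt(3F/96), so f = .16 is F = .0256 × 96/3 = 0.819, p = .486. The average f under no effect is .164. The 90% interval for an observed .16 runs from 0 to sqrt(7.40/100) = .27. Both measures pass in .486² = 24% if independent, and in 27% at correlation .5.

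**2. Partial f at target.** With arm values 0, d, d, d, the SD is d × sqrt(3/16), giving .231 (BOLD) and .297 (gamma). Noncentrality is 100 × SD², or 5.35 and 8.85. Pass probabilities are .901 and .969, product .87. Simulated: 87-88%, whatever r is.

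**3. Cell-mean f at target.** f = SD(dz across arms) × sqrt((1 − r)/2). At r = .5 the factor is .5, so f = .116 and .149. The target-implied f equals .16 at r = 1 − 2(.16/SD)², which is .042 for BOLD and .421 for gamma. At any higher r the target lies below the bar. At r = .5, taking f = ½ sqrt(3F/100), the bar is F ≥ .32² × 100/3 = 3.41. Pass probabilities are .312 and .544, product .17. Simulated: about 17-24%. Taking ½ sqrt(3F/96) instead, the bar is F ≥ 3.28 and the range 19-26%.

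| Assumed r | Both pass at target, cell-mean f |
|---|---|
| 0 | about 60-65% |
| .2 | about 46-54% |
| .5 | about 17-24% (19-26% with 3F/96) |
| .7 | about 2-5% |

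**4. Direction rule, on partial f with no tDCS effect.**

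| What must be positive on both measures | Go |
|---|---|
| Nothing | 24-27% |
| Top current's own pre-to-post change | 14-22% |
| Same, all arms including sham changing by an assumed dz of .2 | 21-27% |
| At least one current above sham | 11-17% |
| Pooled active above sham | 6-10% |
| Every current above sham | 1.5-4% |

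The top current here is the one with the highest mean dz. A change common to all arms cancels in the sham comparisons.

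Requiring at least one current above sham leaves Go at target at 87-88%. It leaves Go at 79-81% for a linear pattern (0, .6, .8 and 1.0 of target). If only one arm is at target, Go is 85-86% with the requirement and 87-88% without it. The two strictest rules cost far more in that last case: about 59-64% for pooled active and 10-17% for every current (BOLD-gamma correlation 0 to .6).

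**5. Ranking.** BOLD and gamma put different currents first in 49-67% of trials with all active arms at target, and in 42-57% with the linear pattern.

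**The case against.** Group-by-time is the natural term. The rule asks for an effect of tDCS and for confirmation that tDCS drives it. A reader might infer that the time main effect, which includes sham change, could satisfy the bar. That wording does not support it, and nothing here rests on it.

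A reader might also infer that direction is not handled at all. That is too strong. Direction is a separate step after f, and the plan supplies signed tools: active against sham, within-group change and polynomial trends. What stays open is which contrast governs and in how many arms. Likewise dz is defined for each group; only its combination across two measures is missing.

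The target scenario is a model. The dz values are called ideal, and the Hypothesis section expects the greatest engagement at 2.5 mA, not a flat pattern. With two arms at target and r = .5, cell-mean f is .134 for BOLD and .172 for gamma, so gamma clears the bar. The value of r is assumed, which is why a range is shown.

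Cell-mean f may well be what was meant. At N = 100, an f of .16 has power .75 on that reading at r = .5, against .23 as partial f (two-sided alpha of .05 assumed). The documents do not say so, and that reading conflicts with the dz targets at moderate r.

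Finally, an early-phase gate may accept a generous false-Go rate. That is the sponsor's choice and the documents set no limit. It is still a choice that the text should make visible.

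**Conclusion.** The point stands and should be fixed before unblinding. The Go rule names neither the formula for f nor the contrast that shows direction. On partial f the bar sits at the null average: both measures pass in 24-27% of trials with no effect, before a direction check, and in 87-88% at target. On cell-mean f at r = .5 the bar lies above what the plan's own targets imply, and about 17-24% pass at target. If the within-group change of the top current alone settles direction, null Go on partial f is 14-22%, or 21-27% with a shared change of dz .2.

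These sizes rest on the assumptions listed in the check. The cell-mean figure in particular moves from about 60-65% at r = 0 to 2-5% at r = .7.

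A reader might take 24-27% as the trial's false-Go rate. The documents do not support that: a direction step follows, and completion is a further condition for starting R33.

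**What to change.** In the Phase Transition Criteria, and in the matching selection rule in Background, before unblinding:

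1. State that f is the group-by-time effect and give its formula. If cell-mean f is meant, state the assumed pre-post correlation and reconcile .16 with the dz targets.
2. State that Go requires f ≥ .16 on both measures and at least one current that meets the completion criterion and whose post-minus-pre change exceeds that of sham on both measures. The comparison is already planned under Primary Objective.
3. State how the BOLD and gamma dz are combined to rank currents.
4. Report f with its confidence interval.

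The completion criterion itself needs reconciling. It is above 80% in Background and the Phase Transition Criteria, but 80% in Hypothesis and under Tertiary Objective. With 25 per arm, 20 completers meet one and fail the other.

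The cost is a short wording change and a slightly stricter Go rule. On partial f, item 2 lowers null Go from 24-27% to 11-17%, with at most about two points lost in the effect patterns checked.

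Two further options are trade-offs for the sponsor. A bias-corrected bar, f² = 3(F − 1)/N, needs F ≥ 1 + .0256 × 100/3 = 1.85. Its null Go is about 2-4% alone and 1-2.5% with item 2, but Go at target falls to 55-59%. Requiring omnibus p < .05 (partial f ≥ .29) gives null Go of about 0.2-0.9% alone and 0.1-0.6% with item 2, with Go at target 31-37%.

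### The rule for choosing the R33 current strength ranks on a single effect size, but each strength has two (BOLD and gamma), and the both-measures condition is not tied to the strength chosen

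*Combined protocol and SAP*

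**What the plan says.** The paragraph on R61 to R33 Phase Transition Criteria, under STATISTICAL METHODS, has two steps.

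- **Go bar.** A single tDCS effect must reach f ≥ .16, and this is asked "for both DLPFC BOLD signal and frontal EEG gamma activity".
- **Selection.** The choice of strength comes next: "After confirming that this effect is driven by tDCS effects in a positive direction, the current strength that has the highest effect size" is carried into R33, on condition that more than 80% of its participants complete.

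BACKGROUND repeats the selection step in nearly the same words, closing with "will be the one that is selected for the R33 phase", and names no measure either.

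Two other paragraphs of STATISTICAL METHODS bear on what effect size means here:

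- **Primary Objective** puts the f target next to the omnibus analysis: "Group and time point differences will first be assessed with omnibus tests instantiated through the general linear model (e.g., repeated measures ANOVA"). It also plans post-hoc comparisons of each active group with sham.
- **Secondary Objective** gives a per-strength measure, Cohen's d_z, which "will be calculated within each group based on the difference between control-related activations from the pre- and post-test assessments". The targets, described as ideal, are .534 for BOLD and .687 for gamma.

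The Hypothesis section expects 2.5 mA to show the greatest engagement on both measures.

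**The concern.** The selection step assumes that each strength has one effect size. The Secondary Objective gives each strength two, and the comparisons with sham offer a further possible metric. The plan does not say which one ranks the strengths, how BOLD and gamma combine, or what happens when they rank the strengths differently.

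The both-measures condition is worded for an effect of tDCS, not for the strength that goes forward. Completion is the only condition tied explicitly to the selected strength. If f comes from the omnibus test, BOLD can reach the bar because of one strength and gamma because of another, so that Go is met although no single strength engages both targets.

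The choice of one strength is the practical output of R61, and BACKGROUND builds R33 on improvement mediated by both DLPFC and frontal gamma. An incomplete rule leaves that choice to be made after the data are seen.

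**Working it through.** **Plan's own figure.** The bar f ≥ .16 is stated without alpha, power or pre–post correlation, so there is no stated calculation to reproduce. The point is about logic. The arithmetic below shows that the gap can occur, and roughly how often.

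**Inputs from the documents.** Four groups (sham, 1.5, 2.0, 2.5 mA) of 25; f ≥ .16 on both measures; d_z targets .534 (BOLD) and .687 (gamma); completion above 80%.

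**Assumptions, not in the documents.** Change scores with unit SD, the true effect patterns below, and a BOLD–gamma correlation of change scores from 0 to .5.

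**1. Can Go be met with no strength engaging both targets?** Take true mean changes, in SD units, for sham/1.5/2.0/2.5 mA:

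- BOLD: 0 / 0 / 0.8 / 0
- Gamma: 0 / 0 / 0 / 0.8

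For each measure the grand mean is 0.2, and f is the SD of the four group means over the SD of change: f = √[(3 × 0.2² + 0.6²)/4] = √(0.48/4) = .346. Both measures clear .16 with effects in the positive direction. BOLD names 2.0 mA, gamma names 2.5 mA, and each of these has zero effect on the other measure.

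The example depends on the convention for f. On the repeated-measures scale, f × √((1 − ρ)/2) gives .346 × √.25 = .173 at ρ = .5, which passes, and .346 × √.15 = .134 at ρ = .7, which fails.

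**2. How often do the two measures name different top strengths?** Simulation, 40,000 trials per scenario, ranking on within-arm d_z:

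| True pattern | Different top strength (correlation 0 to .5) |
|---|---|
| All three strengths at target | about 67% to 49% |
| Effects at 1/3, 2/3 and 1 of target | about 44% to 32% |
| Only 2.5 mA active, at target | about 5–8% |

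The first row at zero correlation is what chance gives: 1 − 3 × (1/3)² = 2/3. Ranking on the sham-referenced difference instead changes little: 67% to 47% for the first row and 41% to 30% for the second. The middle row depends on the steps assumed. Effects proportional to mA (.6, .8, 1 of target) give 57% to 42%; effects at 0, .5 and 1 give 28% to 21%.

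**3. Split engagement (illustrative).** Let 1.5 mA engage only BOLD and 2.5 mA only gamma. Taking f as the partial f of group by time, both measures reach .16 in about 87% of trials. The plan also requires a positive direction. With a lenient version of that check (pooled active mean above sham on both measures), the share falls to about 58–62%. In about 97% of those trials the two measures name different strengths.

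**4. Does the completion condition settle it?** With 25 per group, 20/25 is exactly 80%, so exceeding 80% needs at least 21 completers. The binomial probability is .42, .68 and .90 at true completion rates of 80%, 85% and 90%. Several strengths can qualify, so completion does not break the tie.

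**The case against.** The case against has real force on size, less on substance.

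- **The largest rate costs least.** If the strengths are truly equal, disagreement is mostly chance and either choice gives the same true engagement. If 2.5 mA alone is active, a case in line with the hypothesis, disagreement is only about 5–8%. Both limits stand. But a plan that tests three strengths because the best is unknown cannot rely on its hypothesis to make the rule unambiguous.
- **The trial-level reading of f is an inference.** The transition paragraph does not say how f is computed. If f were meant per strength, the split-engagement problem would weaken. The ranking gap would remain.
- **Other analyses would show a weak strength.** Comparisons with sham, within-group tests, d_z on each measure and trend analyses are all planned. They would make a missed target visible, but none supplies a ranking rule.

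A reader might draw three stronger conclusions that the documents do not support:

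- That split engagement passes Go 87% of the time. This leaves out the stated direction check.
- That a strength failing completion hands its Go to the next strength. The text joins the two conditions with *and*; taking the next strength is one possible reading, and not the more natural one.
- That a selected strength below .534 or .687 breaks the rule. Those targets are called ideal and are not part of the transition criteria.

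**Conclusion.** The concern holds as a defect in a stated decision rule. The selection step does not define which effect size ranks the strengths, and the both-measures condition is not tied to the strength selected. No other section repairs either gap.

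The textual gap needs no assumption. Its frequency does: about 67–49% disagreement with equal strengths, 44–32% with effects rising in thirds, and 5–8% with one active strength, given 25 per arm and an assumed correlation of 0 to .5. That Go can be met by different strengths on the two measures rests on reading f as the omnibus effect size. The documents do not support a claim that the rule will usually carry forward a strength without engagement.

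This should be fixed, but it does not undermine the trial. The primary engagement analysis is unaffected.

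**What to change.** In the transition criteria and in BACKGROUND, restate the selection step:

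1. Name one per-strength metric, computed on both BOLD and gamma, for example the sham-referenced standardised change.
2. Make a strength eligible only if its own estimate is in the positive direction on both measures and it meets the plan's existing completion condition. Apply this before ranking.
3. Rank the eligible strengths by one score fixed before unblinding, for example the mean of the two standardised effects.
4. State that the decision is No-go if no strength is eligible.

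Keep f ≥ .16 as the trial-level bar. Do not turn the ideal d_z targets into per-strength bars. Used as sham-referenced bars, they would give a chance of any candidate of about 27–38% with effects rising in thirds and 48–58% with equal effects, against a chance of Go of roughly 74–77% and 87–88% now.

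The cost is a few sentences, no new data and a slightly harder Go. The limit is that a positive estimate is a weak requirement: a strength with no true effect on a measure relative to sham still shows one half the time, by symmetry. The change makes the choice unique and pre-set. It does not prove that the chosen strength engages both targets.
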